6) Gait Analysis: Subjects will wear sensors on their hands, arms, chest, trunk, feet and legs(APDM System). These tasks will quantify measures such as gait asymmetry, gait rhythmicity and left-right step coordination during subjects normal walking. Subjects may be asked to do regular forward walking as well as walking around obstacles (such as chairs, or small room dividers). These obstacles will be used in order to elicit freezing, which often occurs in constrained spaces. This type of freezing is frequently encountered in subjects' daily lives. Subjects will be monitored carefully by research team in order to ensure their safety and comfort.

7) Vibrotactile Stimulation: Patients will wear the gloves at rest or during kinematic movement analysis described above. If patients report pain or discomfort associated with the gloves, they will be taken off immediately. We do not anticipate this to occur.

The Local Field Potentials (LFP) from the DBS leads (electrodes) will be recorded during each kinematic test using the new sensing capabilities of the implanted neurostimulator (Activa PC+S). The LFP data will be retrieved from the neurostimulator during each kinematic test. The Nexus-D and Nexus E Systems will be used. Nexus-D and Nexus-E establishes a connection between the implanted neural electrodes and an external computer or their

implanted INS (the device in the patient's chest). This will allow for recording of neural activity in real time and adjustment of stimulation within clinically safe limits using prewritten algorithms that respond to real time neural and kinematic recordings. Real time STN LFP beta band power will be calculated both OFF DBS, and during "therapeutic" DBS. DBS will be applied through the electrode (1 or 2) that lies in between the electrode pair (0-2 or 1-3) with the greatest beta power. Therapeutic DBS: 100-190 Hz, 60 microsec at 3 volts OR the highest voltage <3V, that does not cause adverse effects. We will confirm that the therapeutic DBS will attenuate rest beta power by $\geq 50\%$. Patients will be seated at rest, or while performing self-paced repetitive wrist flexion-extension (WFE) for periods of 10 seconds, after a "Go" signal with angular velocity sensors attached to the hand. They may also do other tasks outlined above during closed loop stimulation.

Specific Aim 1a and 2a (SA1a, SA2a): Determination of classifier thresholds:

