SA1. Resting state neural: ON and OFF triggers when the beta band power $> 50\%$ and $< 25\%$ respectively of the resting state beta power differential (beta power OFF – ON therapeutic DBS). SA2. Kinematic, tremor/bradykinesia: ON and OFF triggers when rectified tremor amplitude/root mean square angular velocity (Vrms) of WFE $> 50\%$ or $< 25\%$ of tremor/Vrms differential (OFF – ON therapeutic DBS) respectively.

Specific Aim 1b and 2b (SA1b, SA2b): Outcomes will be measured after 30 minutes of aDBS or cDBS. For neural and tremor aDBS, the Activa® PC+S will be updated in real time. For bradykinesia aDBS, the Activa® PC+S will be updated with the Vrms from 10 second epochs of WFE that the PD subject will perform every 2 minutes during the 30 minute trial. At the six month visit the subject will come in on medication on stimulation and SA1 and SA2 will be repeated in the then optimized on medication state. The control policy algorithms will be adjusted as necessary to adapt to this state (Specific aim 3, SA3) At the 1, 3, 6, 9 and 12 month visits subjects will come in off medication and on stimulation and will repeat quantitative assessment of motor function. This may include quantitative digitography (QDG), quantitative range of motion analysis (Motus, LG G Watch, APDM System), tremorography, surface electromyography (EMG), and computerized dynamic posturography and UPDRS III. The subject will perform these assessments in the on clinical stimulation state and will repeat all or a subset of these tests in the off stimulation state. Subjects may continue these motor tests after the 12 month visit during their regularly scheduled clinic visits. Most often, this is every 3 months, however, patients may come in more or less often, depending on their clinical schedules.

For subjects already enrolled in eprotocol 25916:

Subjects who have been implanted with the Activa PC+S Neurostimulator system and who are enrolled or who have completed the Brain Radio initial study may be asked to consent to Nexus study. They will be asked to come in for additional visits (may be at follow-up if still enrolled or an additional study session.) These participants may complete the specific aims 1,2,3 listed in above protocol in addition to collecting data recordings with Nexus-D and Nexus-E systems.

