### **Analysis of primary outcome**

The number and percentage of occurrences of treatment-related adverse events (AE) will be reported for each treatment arm of continuous DBS (cDBS), adaptive DBS (aDBS) and off DBS.

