### **Analysis of secondary outcomes**

For Alpha/beta power and Sample Entropy (SampEn): Alpha/beta power varied across subjects sometimes by orders of magnitudes. Relative alpha and beta power was calculated by dividing the summed absolute alpha or beta power by the summed power in the 40- 70 Hz band during the resting state, and allowed comparison across subjects, whose raw signal magnitude can vary by one or two orders of magnitude, see Supplementary information. The FW task was analyzed by excluding the turning periods at the end of the 10 m of straight walking. As a result, each FW task had 4 trials.

Similarly, as the TBC task had four trials, it was also analyzed as four separate time periods for each patient. The SIP task had one trial per patient. Asymmetry and arrhythmicity were assessed individually using a linear mixed effect model in Freezers and Non-Freezers during FW, while a one-way ANOVA was used in SIP. A one way ANOVA and a Kruskal-Wallis test by ranks was also used to determine if alpha or beta power and SampEn changed significantly between Freezers and Non-Freezers in SIP, while a linear mixed effects model was used for both TBC and FW, in order to account for the four trials. Freezer or Non-Freezer type was a fixed effect and a factor variable with 2 levels (Freezer and Non-Freezer). Subject STN was a random effect, and a random intercept was used in the model. Residuals were assessed for homoscedasticity and normality, and all statistical assumptions were met.

To compare arrhythmicity, asymmetry, or stride time between groups, a one-way ANOVA was used. Paired t-tests were used to compare the effects of different stimulation frequencies on arrhythmicity, asymmetry, and stride time within each group for each task. Post hoc analyses were completed to compare between stimulation conditions. All statistical testing was performed in SigmaPlot (Systat Software, San Jose, CA) using two-tailed tests with significance levels of  $P < .05$ .

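### The only paired stimulation test named in the SAP's analysis sections compares stimulation frequencies, a within-patient comparison that the protocol does not define

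*SAP*

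**What the plan says.** **SAP, Analysis of secondary outcomes.** The within-patient test of stimulation is given as: "Paired t-tests were used to compare the effects of different stimulation frequencies on arrhythmicity, asymmetry, and stride time within each group", separately by task. The groups are Freezers and Non-Freezers. The next sentence adds: "Post hoc analyses were completed to compare between stimulation conditions". All tests are run "using two-tailed tests with significance levels of" P < .05.

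**SAP, Analysis of primary outcome.** Adverse events are tabulated for "each treatment arm of continuous DBS (cDBS), adaptive DBS (aDBS) and off DBS".

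**SAP, Power analysis.** The sample size rests on a paired t-test of the number of freezes, comparing no or ineffective stimulation with effective stimulation.

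**Protocol 2.a, Procedures.** Frequency enters as a stimulation parameter once: "Therapeutic DBS: 100-190 Hz, 60 microsec at 3 volts OR the highest voltage <3V, that does not cause adverse effects". For Specific Aims 1b and 2b the compared runs are: "Outcomes will be measured after 30 minutes of aDBS or cDBS". At the 1, 3, 6, 9 and 12 month visits, patients are assessed on their clinical stimulation, and all or some of the tests are repeated with stimulation off.

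**Protocol 1.b and 1.c.** The objectives compare aDBS with cDBS, and kinematic aDBS with neural aDBS and/or cDBS. The control algorithm switches the device on or off at a preset setting.

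**The concern.** A paired t-test needs two defined conditions observed in the same patient. The SAP names stimulation frequency as what separates the two, but the protocol describes no run in which one patient receives two frequencies for comparison. A reader therefore cannot tell which recordings enter the test, at which visit they were made, or whether they come from this protocol. The last point is a live one, because up to 15 subjects may also be enrolled in eprotocol 25916.

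The protocol asks whether aDBS is more efficient and effective than cDBS. The one paired stimulation test that the SAP spells out asks something else. If it is followed literally, the P values reported for stimulation would not answer Objectives 1 to 3, while the contrast that would answer them has no stated test.

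**Working it through.** **1. The conditions, set side by side.**

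| Place | What distinguishes the conditions | Does frequency vary within a patient? |
|---|---|---|
| Protocol 1.b, Objectives | aDBS or cDBS; neural or kinematic classifier | Not stated |
| Protocol 1.c, Rationale | Stimulation switched on or off at a preset setting | No |
| Protocol 2.a, therapeutic DBS | A setting within 100-190 Hz | A permitted range, not a set of test levels |
| Protocol 2.a, Aims 1b and 2b | 30-minute runs of aDBS or cDBS | Not stated |
| Protocol 2.a, follow-up visits | Clinical stimulation on or off | Not stated |
| SAP, primary outcome | cDBS, aDBS, off DBS | Not stated |
| SAP, paired t-tests | Stimulation frequency | Yes |

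Only the last row makes frequency the factor, and no other row supplies levels for it.

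**2. Can another SAP passage supply the missing contrast?** There are two candidates.

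*The paired t-test in the Power analysis.* Its figure reproduces. The inputs there are a mean of 4.9 freezes, SD 2.47, 65% improvement, alpha 0.05, power 0.80, and 87% of patients freezing.
- Difference: 0.65 x 4.9 = 3.185 freezes.
- Standardised effect: 3.185 / 2.47 = 1.289, taking 2.47 as the SD of the paired difference.
- The two-sided paired t-test (noncentral t) needs n = 7, with power 0.81.
- Allowing for 87% who freeze: 7 / 0.87 = 8.05, rounded up to 9, which is the SAP's figure.

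So the 9 subjects belong to a contrast of no or ineffective versus effective stimulation on the number of freezes. No analysis section carries that test out. The figure does not cover a frequency contrast, nor arrhythmicity, asymmetry or stride time.

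*The post hoc comparison between stimulation conditions.* The SAP gives no test, outcome, pairing or list of conditions for it. It might be paired and might use the protocol's own conditions, but the text does not say so.

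Neither passage supplies a stated paired test of aDBS against cDBS or against off.

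**3. How many tests are affected.** From the SAP:
- Measures: arrhythmicity, asymmetry and stride time = 3.
- Groups: Freezers and Non-Freezers = 2.
- Tasks: FW, TBC and SIP = at most 3.

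3 x 2 x 3 = 18 paired tests for each pair of frequencies. This is an upper limit, because the SAP says each task without listing which tasks it means. The total cannot be fixed, because the number of frequencies is not given.

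**The case against.** Four points can be made for the plan.

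*The word may simply be loose.* The paragraph is in the past tense and points to supplementary information, so it may describe analyses already done, with frequency standing in for condition. That is possible. It changes the explanation, not the need for correction: as written, the reader still cannot tell which runs are compared.

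*Other stimulation comparisons exist.* This is correct, and it limits the claim to the only paired stimulation test named in the analysis sections. The post hoc sentence and the Power analysis do not fill the gap, for the reasons given in the working.

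*Several frequencies could have been given at one visit.* A reader might infer that the frequency tests must either have no data or compare frequencies across visits, and so be confounded with time since implant, medication change and disease course. The documents do not support that. They describe no frequency change between visits. They allow stimulation to be adjusted within safe limits during a session, and additional study sessions for some patients, so same-visit frequency runs are undescribed but not excluded. The follow-up motor assessments are done off medication, and inclusion criterion 4 asks for an unchanged dose, where possible, once DBS is optimized. Nor can a false-positive rate be attached: it would need an assumed time shift and the sizes of the two groups, and the documents give neither.

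*The tests are secondary.* This is true. The primary outcome, adverse-event counts by cDBS, aDBS and off DBS, is untouched.

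**Conclusion.** The concern holds as a mismatch between a stated analysis and the design. The SAP's named paired test uses a factor that protocol 2.a does not define as a comparison. It affects up to 18 secondary tests per pair of frequencies, none of which has protocol-defined levels, a sample-size basis in the documents, or a bearing on the aDBS versus cDBS objectives. The count assumes that all three tasks named in the SAP are meant.

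The conclusion rests on the text alone. The correct description of the frequency factor is undefined: the documents show neither that the tests would be empty nor that they would be biased by time. The point should be settled before secondary results are reported, but it does not affect the primary outcome.

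**What to change.** Reconcile the SAP's Analysis of secondary outcomes with protocol 2.a.

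- Make the protocol's own run conditions (off, cDBS and aDBS) the levels of the paired within-patient test, and identify aDBS versus cDBS as the contrast that answers the objectives. Say whether neural and kinematic aDBS are kept apart, as Objective 2 requires.
- For the post hoc comparison between conditions, state the test, the outcome and the pairing, or fold it into the test above.
- If frequency runs were really done, name the runs and their source protocol, report them as a separate question, and pair only conditions given at the same visit.

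The cost is SAP wording, with a short protocol amendment only if frequency runs are intended. No extra patients are needed. The sponsor gives up any frequency result that the protocol does not support.
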